7.12. Analyses of Biomarker Data

7.12.1. Analyses of florbetapir (Amyloid PET Imaging) Data

7.12.1.1. Placebo-Controlled Period

Analyses of the standardized uptake value ratio (SUVr) of all florbetapir parameters including the following parameters will be conducted:

- Composite SUVr and centiloids and
- SUVr in frontal, temporal, parietal, and cingulate brain regions.

The full list of florbetapir parameters is provided in [Appendix 1](#).

The conversion of SUVr value to centiloid value is based on the following formula: Florbetapir centiloids = $183.07 * \text{Florbetapir SUVr} - 177.26$.

Analysis of the change from baseline to endpoint of each florbetapir parameter will be done. The analysis will be done using an analysis of covariance (ANCOVA) model with fixed effects of baseline florbetapir result, treatment, APOE4 Carrier Status (yes/no), and age at baseline. The null hypothesis is that the difference in least square mean between the solanezumab group versus placebo equals zero.

Because of the challenges associated with scheduling and obtaining a PET scan, some endpoint PET scans were obtained after the initiation of open-label dosing. Analyses specified above will be conducted in which these observations are removed.

Additionally, due to the disassociation of visit and time caused by the COVID disruption, an analysis treating time as a continuous variable will be conducted. Each florbetapir parameter will be regressed on time, treatment, APOE4 Carrier Status (yes/no), and age at baseline, with the constraint that the two treatment groups have the same y-intercept. Slopes between the two treatment groups will be compared.

To assess the relationship of florbetapir parameters and efficacy outcomes with treatment, Spearman's rank correlation coefficient will be obtained on change from baseline to endpoint for the florbetapir composite SUVr with change from baseline to endpoint for PACC, ADL-Prevention Questionnaire, CFI, CDR-SB and C3. These correlations will be obtained separately within each treatment group and for all participants.

7.12.1.2. Open-Label Period

Florbetapir is not collected during the open-label study period.

7.12.2. Analyses of flortaucipir (Tau PET Imaging) Data

7.12.2.1. Placebo-Controlled Period

Analyses of the standardized uptake value ratios (SUV_r) of all flortaucipir scans will be conducted. An NCS analysis will be used to assess the difference between treatment groups in change from baseline in SUV_r at 240 weeks. Time will be treated as a continuous variable with values equal to the years between baseline and follow-up PET scans. We will assume an unstructured covariance structure. The NCS basis expansion will assume an interior knot at the median of observation times, and boundary knots at zero years and the maximum follow-up. The fixed effects will include the following terms: (i) NCS basis expansion terms (two terms), (ii) NCS basis expansion terms-by-treatment interaction (two terms), (iii) baseline flortaucipir SUV_r, (iv) APOE4 Carrier Status (yes/no), and (v) age. The model is constrained to not allow a difference between treatment group means at baseline.

The list of composite brain regions for flortaucipir is provided in [Appendix 1](#). The SUV_r for each composite region will be defined as the voxel-weighted counts from the included component regions divided by the counts for the cerebellum crus region. The composite region called Middle will be considered the primary area of interest, with the other 7 regions being considered secondary.

The null hypothesis is that the treatment difference between solanezumab and placebo for the SUV_r at 240 weeks is equal to zero. The analysis will be carried out in the population of participants that are randomized and have a baseline score and at least 1 post-baseline assessment. If the unstructured covariance structure matrix results in a lack of convergence, the same order of covariance structures specified for the primary analysis will be used.

To assess the relationship of flortaucipir parameters and efficacy outcomes with treatment, Spearman's rank correlation coefficient will be obtained on change from baseline to endpoint for each flortaucipir parameter with change from baseline to endpoint for PACC, ADL-Prevention Questionnaire, CFI, CDR-SB and C3. These correlations will be obtained separately within each treatment group and all participants.

7.12.2.2. Open-Label Period

Changes in the standardized uptake value ratio (SUV_r) during open-label treatment of all flortaucipir composite brain regions specified in Appendix 1 will be described.

7.12.3. Analysis of Plasma A β and Plasma pTau-217

7.12.3.1. Placebo-Controlled Period

To evaluate the change in plasma A β analytes (including assayed plasma A β ₁₋₄₀ and assayed plasma A β ₁₋₄₂) and plasma pTau-217 after treatment, an ANCOVA will be used to compare change from baseline to each of the post-baseline visits at which plasma analytes are assayed (week 12 and week 240). This analysis will be done separately for each plasma parameter. The model for the fixed effects will include the following terms: (i) baseline plasma value, (ii)

treatment, (iii) APOE4 Carrier Status (yes/no), and (iv) age. The null hypothesis is that the difference in least square mean between the solanezumab group and placebo equals zero.

Additionally, due to the disassociation of visit and time caused by the COVID disruption, an analysis treating time as a continuous variable will be conducted. Each plasma parameter will be regressed on time, treatment, APOE4 Carrier Status (yes/no), and age at baseline, with the constraint that the two treatment groups have the same y-intercept. Slopes between the two treatment groups will be compared.

To assess the relationship of plasma parameters and efficacy outcomes with treatment, Spearman's rank correlation coefficient will be obtained on change from baseline to endpoint for each plasma A β parameter with change from baseline to endpoint for PACC, ADL-Prevention Questionnaire, CFI, CDR-SB and C3. Additionally, the correlation between plasma pTau-217 and both amyloid PET and tau PET will be examined. These correlations will be obtained separately within each treatment group and for all participants

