9.4. Rationale for Selection of Doses in the Study

The A4 study was initiated with active drug of solanezumab 400 mg given intravenously every 4 weeks (400 mg Q4W). Selection of the 400 mg Q4W dose was based largely but not entirely upon the peripheral sink hypothesis, which held that maximizing peripheral target engagement would change Aβ equilibria, resulting in altered amyloid deposition in the central compartment, ultimately leading to a slowing of disease progression. The 400 mg Q4W dose was selected to lower free plasma Aβ concentrations by at least 90%, a level that exceeded what had been associated with slowing of amyloid plaque deposition in transgenic rodent species.

The primary endpoint was not met in the recently concluded Phase 3 Study LZAX of solanezumab 400 mg Q4W in subjects with mild dementia due to AD, defined by a baseline MMSE score of 20 to 26. Subjects treated with solanezumab did not experience a statistically significant slowing in cognitive decline compared with subjects treated with placebo (p=.095), as measured by the 14-item Alzheimer's Disease Assessment Scale-Cognitive subscale (ADAS-Cog14). The study results, including several secondary clinical endpoints, directionally favored solanezumab, but the magnitudes of treatment differences were consistently small. In general, safety findings were consistent with those observed previously in Studies LZAM and LZAN.

Safety analyses from Studies LZAM and LZAN individually and the pooled LZAM and LZAN data indicated a potential safety signal for a heterogeneous set of cardiac events, but this signal was not confirmed based on data from Study LZAX. As measured by the Columbia Suicide Severity Rating Scale (C-SSRS), suicidal ideation and behaviors were infrequent, but greater frequency was observed among solanezumab- compared with placebo-treated patients in Study LZAX. This safety signal has not been observed in other solanezumab studies. At this time, it cannot be determined whether the imbalance observed in Study LZAX is causally related to solanezumab treatment. Lilly will continue to assess this safety signal in the A4 study. The negative efficacy outcome of Study LZAX suggests that an approach to dose selection based on peripheral target engagement may not predict clinical efficacy in Phase 3 trials. Thus, central target engagement based on biomarkers may provide better predictive value for Phase 3 dose selection.

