Phase 2 solanezumab data suggest greater central target engagement may be achieved with dosing greater than 400 mg Q4W. A dose of 400 mg every week (400 mg QW), which is equivalent to 1600 mg over a 4-week period, was given in Phase 2 Studies LZAJ and LZAK, and showed an increased CSF A β signal and an acceptable safety profile.

Exposure–response analyses were conducted following the completion of Studies LZAM, LZAN, and LZAX, but given that only a single dose level was administered in these studies, no compelling relationship between exposure and change in various cognitive endpoints could be discerned.

Biomarker data from patients receiving LPs in Studies LZAM, LZAN, and LZAX suggest that the effect of solanezumab on A β_{1-40} and A β_{1-42} species in the CNS (central target engagement) was present but relatively modest in those studies. Total A β concentrations tended to increase with increasing solanezumab concentrations in the CSF, without reaching an apparent plateau, suggesting that higher solanezumab exposures in the CNS would lead to higher levels of target engagement. Indeed, total A β_{1-40} and A β_{1-42} concentrations were observed to be substantially higher, with a dose of 400 mg QW examined after 12 weeks of dosing in the Phase 2 Study LZAJ, as compared with the Q4W dosing regimen.

To date, the pharmacokinetics (PK) of solanezumab have been explored in single doses up to 10 mg/kg (approximately 700 mg), or multiple doses of up to 400 mg QW. The PK of solanezumab have been linear with respect to dose, and stationary with respect to time. Accordingly, the average plasma solanezumab concentration over 4 weeks at a dosing regimen of 1600 mg Q4W would be anticipated to be equivalent to the exposure over 4 weeks at the previously tested 400 mg QW dosing regimen. This projected exposure is less than the no-observed-adverse-effect level (NOAEL) exposure determined in monkeys as part of a 12-month chronic toxicology study. Assuming linear PK, the projected C_{max} at 1600 mg Q4W is anticipated to provide an exposure multiple that is similar to that calculated for the projected average concentration.

Solanezumab was well tolerated in monkeys, with no adverse effects observed at the maximum dose studied, 100 mg/kg. Solanezumab exposures at 1600 mg Q4W were projected using

clinical data collected at 400 mg Q4W. These exposure estimates provide a 5.8X multiple to the exposures in monkeys at the 100 mg/kg dose.

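### For plasma Aβ, the added common-intercept straight-line model would show only about 5% of an early, lasting effect at Week 12 and would tilt the placebo line, so its slope difference is not a rate of drug effect

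*SAP*

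**What the plan says.** SAP 7.12.3.1 covers assayed plasma Aβ1-40, Aβ1-42 and pTau-217, measured after baseline at Weeks 12 and 240. It specifies two analyses.

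- First, "an ANCOVA will be used to compare change from baseline to each of the post-baseline visits", separately for each analyte.
- Second, because the COVID disruption separated visit from elapsed time, "Each plasma parameter will be regressed on time, treatment, APOE4 Carrier Status (yes/no), and age at baseline", under the "constraint that the two treatment groups have the same y-intercept". The test is then: "Slopes between the two treatment groups will be compared".

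The second analysis has no spline, step or visit term, and no within-participant covariance is stated for it. SAP 7.2 says that analyses with continuous time use every post-baseline observation of the placebo-controlled phase, so the Week 12 sample enters along with baseline and Week 240. For PACC (7.9.1.1) and tau PET (7.12.2.1), the SAP instead uses two spline terms with treatment interactions.

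On the expected effect, Protocol 9.4 says 400 mg was chosen to lower free plasma Aβ "concentrations by at least 90%, a level that exceeded what had been associated with slowing of amyloid plaque deposition" in rodents, and that the pharmacokinetics have been "linear with respect to dose, and stationary with respect to time". Protocol 10.1.3.2 says plasma Aβ is analysed to confirm the drug's pharmacodynamic effect.

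**The concern.** Two straight lines from one intercept fix the shape of the treatment effect. Whatever the fitted difference is at Week 240, the difference at Week 12 must be 12/240 = 5% of it. That may suit a marker that drifts slowly. It does not suit a marker that responds to drug level. By the Week 12 sample a participant on schedule has had three infusions (Weeks 0, 4 and 8), and a response that follows drug level should be largely visible by then, changing later mainly with dose.

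The same sentence is used for florbetapir and CSF, which have only a baseline and an endpoint measurement, so a straight line has no intermediate shape to get wrong. Plasma has an early third time point, and there the shape matters.

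What is at stake is a supportive estimate. The model could report a steady yearly drug effect on Aβ that does not exist, almost nothing at the visit where target engagement should first be seen, and a time trend in untreated participants. Because it was added to deal with the hiatus, it may be cited when the timing of the ANCOVA visits is questioned.

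**Working it through.** The documents give no effect size, power or sample size for plasma, so there is no figure of the plan's own to reproduce. The check is the expected fit of the stated model to a known truth.

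**Inputs.** Sample times t = 0, 12 and 240 weeks (SAP 7.12.3.1 and 7.2); equal arms (1:1, SAP 6.1). Assumed truth: placebo means 0, 0, 0; solanezumab means 0, D, D.

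**Model.** Placebo a + b0·t; solanezumab a + b1·t. Over the three times, Σt = 252 and Σt² = 12² + 240² = 57,744.

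**Least squares, slope difference.** b1 − b0 = D(12 + 240)/57,744 = 0.004364 D per week.

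- Fitted difference at Week 12: 12 × 0.004364 D = 0.052 D (truth D).
- Fitted difference at Week 240: 240 × 0.004364 D = 1.047 D (truth D).

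**Least squares, intercept and placebo.** The slopes are b0 = −252a/57,744 and b1 = 252(D − a)/57,744. Setting the residual sum to zero gives 2D = 6a + 252²(D − 2a)/57,744. Since 252²/57,744 = 1.09975, a = (2 − 1.09975)D/(6 − 2.1995) = 0.237 D (truth 0). The placebo change over 240 weeks is −240 × 252 × 0.237 D/57,744 = −0.248 D (truth 0).

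**Within-person correlation.** Because the SAP states no covariance, the same fit was repeated by generalised least squares with compound symmetry. The intercept stays at 0.237 D throughout.

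| Correlation | Difference, Week 12 | Difference, Week 240 | Placebo change |
|---|---|---|---|
| 0 (least squares) | 0.052 D | 1.047 D | −0.248 D |
| 0.3 | 0.041 D | 0.825 D | −0.137 D |
| 0.5 | 0.036 D | 0.722 D | −0.086 D |
| 0.7 | 0.032 D | 0.642 D | −0.046 D |
| 0.9 | 0.029 D | 0.579 D | −0.014 D |

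**Other scenarios (least squares).**

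- With 30% of Week 240 samples missing (the attrition assumed in SAP 6.2): 0.053 D and 1.068 D.
- With the last sample 9 months, or about 39 weeks, late (Week 279): slope difference D(12 + 279)/(12² + 279²) = 0.003731 D per week, giving 0.045 D at Week 12 and 0.896 D at Week 240. Late sampling does not repair the shape.
- With an effect of R × D at Week 240, the slope difference is D(12 + 240R)/57,744. R = 2 gives 0.102 D and 2.045 D; R = 4 gives 0.202 D and 4.040 D. For a 90% lowering, R cannot exceed 1/0.9 = 1.11, which gives 0.058 D at Week 12.

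**Comparison.** The ANCOVA estimates D at each visit. A model with separate Week 12 and Week 240 differences fits the assumed means exactly, with intercept 0 and a flat placebo arm.

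**The case against.** The strongest objection is that the shape is assumed. Protocol 9.4 gives the reason for choosing a dose and no time course; its statement about time describes the pharmacokinetics of solanezumab, not the Aβ response. The SAP does not say whether the assay measures free Aβ, to which the 90% refers, and the dose rose during the study. This stands. An early level shift is a reasonable inference from the documents, not a fact stated in them.

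Second, the SAP section does not list which samples enter the regression. With baseline and Week 240 alone, the line would recover the Week 240 effect exactly. SAP 7.2 answers this, because continuous-time analyses use every post-baseline observation.

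Third, the stakes are modest. The ANCOVA at each visit is kept. Plasma Aβ is an exploratory objective (SAP 5.3), and everything other than the PACC analysis is secondary to it (SAP 7.4). With no drug effect the expected slopes are equal, so no false drug effect arises. This also stands.

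Some stronger readings are tempting but not supported:

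- A reader might infer that the model loses 80 to 95% of the drug effect. That holds only for the fitted difference at Week 12; at Week 240, least squares recovers about 101 to 105%. The 20% figure at Week 12 needs a four-fold later growth, which is not a level shift and is impossible for a 90% lowering.
- A reader might combine the full placebo artefact with the loss at Week 240. They come from different fits: modelling the correlation shrinks the first and produces the second.
- A reader might translate the artefact into a percentage of baseline on placebo. That would apply a free-Aβ figure to an assay not stated to be free.

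**Conclusion.** The point holds for plasma Aβ, on the inference that much of the effect is present by Week 12. The added model cannot represent such an effect. For a flat effect D, its fitted Week 12 difference is about 0.05 D, or 0.03 to 0.04 D once within-person correlation is modelled, so a covariance term does not cure the shape. The Week 240 difference is about right by least squares and falls to 0.58 to 0.83 D at correlations of 0.3 to 0.9. The shared baseline is misplaced by about 0.24 D. The false placebo change is −0.25 D by least squares and shrinks to between −0.14 D and −0.01 D with correlation.

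The slope difference should therefore not be read as a rate of drug effect on Aβ. This is a modest correction to a supportive analysis. It does not touch the per-visit ANCOVA or the primary result, and it does not extend to pTau-217, for which the documents suggest no early level shift.

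**What to change.** For plasma Aβ, replace the common-intercept straight line with a baseline-constrained repeated-measures model that has a stated within-participant covariance and allows separate treatment differences at Week 12 and Week 240. Either of two forms will do:

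- visit terms, with actual elapsed time at the last sample as a covariate to absorb the hiatus; or
- the two-term spline-by-treatment model already used in SAP 7.9.1.1 and 7.12.2.1, whose two terms per arm can fit the two post-baseline times. Only the values near the sampled times should be interpreted.

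This partly repeats the ANCOVA. What it adds is the use of actual time, which was the purpose of the extra analysis. Keep the slope analysis for pTau-217. The cost is one extra parameter per arm, a few lines of SAP text and minor programming; no new data are needed.

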7.12.3.2. Open-Label Period

Plasma A β analytes are not collected during the open-label study period.

7.12.4. Analyses of vMRI Data

Analyses of all the vMRI parameters including the following parameters will be conducted:

- Right hippocampal volume
- Left hippocampal volume
- Right hippocampal volume + Left hippocampal volume
- Right entorhinal volume
- Left entorhinal volume
- Right entorhinal volume + Left entorhinal volume
- Right cortical gray matter volume + Left cortical gray matter volume
- Right lateral ventricle + Left lateral ventricle

7.12.4.1. Placebo-Controlled Period

Analysis of the change from baseline to endpoint of each vMRI parameter will be done. The analysis will be done using an analysis of covariance (ANCOVA) model with fixed effects of baseline vMRI value, treatment, age at baseline, education, APOE4 Carrier Status (yes/no), and baseline florbetapir cortical SUV_r. The null hypothesis is that the difference in least square mean between the solanezumab group versus placebo equals zero.

Additionally, due to the disassociation of visit and time caused by the COVID disruption, an analysis treating time as a continuous variable will be conducted. Each vMRI parameter will be regressed on time, treatment, APOE4 Carrier Status (yes/no), and age at baseline, with the constraint that the two treatment groups have the same y-intercept. Slopes between the two treatment groups will be compared.

To assess the relationship of vMRI parameters and efficacy outcomes with treatment, Spearman's rank correlation coefficient will be obtained on change from baseline to endpoint for each vMRI parameter with change from baseline to endpoint for PACC, ADL-Prevention Questionnaire, CFI, CDR-SB and C3. These correlations will be obtained separately within each treatment group and all participants.

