10.2.11.2. Safety MRI

An additional safety MRI will be conducted at least 7 days after the second dose of 800 mg and at least 7 days before escalating dose to 1600 mg so results of the central read can be reviewed by the site before the escalation. If a study MRI is scheduled within ± 2 months of the dose escalation MRI, the MRI should be conducted according the dose escalation schedule as a substitute for the MRI specified in the main study schedule; an exception is the MRI at endpoint (Visit 66), which should be done according to the Study Schedule regardless of timing relative to dose escalation. If a subject experiences symptoms suggestive of ARIA-E at any time, the investigator may obtain an unscheduled MRI.

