11.2.9.3. Biomarker Outcomes

Analysis of Plasma. Change in plasma A β and P-tau, GFAP, and Neurofilament light chain after treatment will be compared between treatment groups. This analysis will be done separately for each plasma A β and P-tau parameter.

Analysis of vMRI Data. Change in vMRI data after treatment will be compared between treatment groups. This analysis will be done separately for each vMRI parameter.

Analysis of Amyloid PET Imaging. To provide further supporting evidence that solanezumab attenuates the underlying pathologic process in AD, the change in brain amyloid burden obtained using florbetapir PET imaging will be assessed. Parameters from various brain regions of interest as well as a composite brain measure will be compared between treatment groups.

Analysis of Cerebrospinal Fluid. To provide further supporting evidence that solanezumab attenuates the underlying pathologic process in AD, changes in CSF parameters, including total and free A β_{1-40} and A β_{1-42} species and total tau and P-tau peptides, GFAP Neurofilament light chain, will be compared between treatment groups.

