Visit No. ^a :	V6	V9	V12	V15	V18	V21	V24	V27	V30	V33	V36	V39	V42	V45	V48	V51	V54	V57	V60	V63	V66		
Week:	0	12	24	36	48	60	72	84	96	108	120	132	144	156	168	180	192	204	216	228	240		
Tolerance Interval for Visit (days)		±10	±10	±10	±10	±10	±10	±10	±10	±10	±10	±10	±10	±10	±10	±10	±10	±10	±10	±10	±10	±10	
Collection of Laboratory Specimens ^c																							
Clinical chemistry, hematology, HbA1c	X	X	X		X					X					X						X	X	
High sensitivity C-reactive protein	X	X	X		X					X					X						X	X	
Urinalysis					X					X					X						X	X	
Immunogenicity specimen	X	X	X		X					X					X						X	X	
Plasma for solanezumab	X	X	X		X					X					X						X	X	
Plasma for biomarker long-term storage	X	X	X		X					X					X						X	X	
Serum for biomarker long-term storage	X	X	X		X					X					X						X	X	
Whole blood for biomarker long-term storage	X									X					X						X	X	

Abbreviations: AD = Alzheimer’s disease; ADCS-ADL Prevention Questionnaire = Alzheimer’s Disease Cooperative Study – Activities of Daily Living Prevention Questionnaire; PACC = Preclinical Alzheimer’s Cognitive Composite; AE = adverse event; CFI = Cognitive Function Index; CRF = case report form; C-SSRS = Columbia Suicide Severity Rating Scale; EOS = end of study; HbA1c = hemoglobin A1c; LP = lumbar puncture; MRI = magnetic resonance imaging; PET = positron emission tomography; Rand = randomization; RUI-B = Resource Use Inventory, Brief version; SC = screening; V = Visit.

- ^a At all visits not shown on the table (Visits 7, 8, 10, 11, 13, 14, 16, 17, 19, 20, 22, 23, 25, 26, 28, 29, 31, 32, 34, 35, 37, 38, 40, 41, 43, 44, 46, 47, 49, 50, 52, 53, 55, 56, 58, 59, 61, 62, 64, and 65), infusion and collection of AE and concomitant medication information will occur.
- ^b If C-SSRS indicates suicide-related behavior has occurred, the Lilly Self Harm Form is to be completed and follow-up must occur by a site clinician.
- ^c If MRI is done on the same day as cognitive and other assessments, then it should be done after cognitive and other tests. MRI may be done before other visit procedures, including cognitive and other tests, but in that case MRI must be done at least 1 day before other visit procedures. The V66 MRI may be done up to 4 weeks before other V66 procedures, but must be done after the completion of V65.
- ^d Every effort should be made to administer the PACC before all other procedures on the same day. PACC version at early term visit should be the next version in series (not including SC).

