7.1. General Considerations

Unless otherwise noted, all tests of treatment effects will be conducted at a 2-sided alpha level of 0.05; 2-sided confidence intervals will be displayed with a 95% confidence level. All tests of interactions between treatment and other factors will be conducted at an alpha level of 0.05.

All analyses will follow the modified intent-to-treat (mITT) principle unless otherwise specified. An ITT analysis is an analysis of data by groups to which the participants are assigned by random allocation, even if the participant does not take the assigned treatment, does not receive the correct treatment, or otherwise does not follow the protocol. An mITT analysis is an ITT analysis for all participants who have a baseline and at least 1 postbaseline measure. All safety analyses will be done using the safety population. Analysis populations are described below (Section 7.5).

When change from baseline is assessed, participants will be included in the analysis only if both a baseline and a post-baseline measure are available. Unless otherwise defined, a baseline measure is the last non-missing observation collected prior to the first infusion of study medication. End point is the last non-missing post-baseline measurement.

For MMRM analyses, observations collected at non-scheduled visits (see Section 7.2) will not be included in the analyses. For NCS and MMRM analyses, unless otherwise specified, an unstructured covariance structure will be used. If the unstructured covariance structure matrix results in a lack of convergence, the following covariance structures will be used in sequence: heterogeneous Toeplitz covariance structure, heterogeneous autoregressive covariance structure, heterogeneous compound symmetry covariance structure and homogeneous compound symmetry covariance structure.

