Intent-to-Treat Population (ITT)	Tables, Listings, Figures of the following: participant disposition, participant characteristics at baseline, pre-existing conditions, significant historical diagnoses, concomitant medications.
Modified Intent-to-Treat Population (mITT)	Tables, Listings, Figures of the following: PACC, ADL-Prevention Questionnaire, CFI, CDR-SB, CDR Global Score, C3, MMSE, RUI-B, florbetapir parameters, plasma parameters, vMRI parameters, CSF parameters.
Completers Population	Tables, Listings, Figures of the following: PACC, ADL-Prevention Questionnaire, CFI, CDR-SB, C3, MMSE, RUI-B, florbetapir Parameters, plasma parameters, vMRI parameters, CSF parameters.
Safety Population	Tables, Listings, Figures of the following: exposure and infusion, adverse events, laboratory results, vital signs, weight, ECG, MRI, Immunogenicity, Psychological Well-Being, C-SSRS
Per-Protocol Population	Tables, Listings, Figures of the following: participant characteristics at baseline, PACC.

Abbreviations: ADL = activities of daily living; C3 = computerized cognitive composite; C-SSRS = Columbia-Suicide Severity Rating Scale; CDR-SB = Clinical Dementia Rating - Sum of Boxes; CFI = Cognitive Function Index; CSF = cerebrospinal fluid; ECG = electrocardiogram; ID = identification; MMSE = Mini-Mental State Examination; MRI = magnetic resonance imaging; PACC = Preclinical Alzheimer Cognitive Composite ;RUI-B = Resource Use Inventory, Brief; vMRI = volumetric magnetic resonance imaging.

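### The first-listed vMRI ANCOVA takes each participant's last scan as endpoint; with 30% dropout it estimates about 82% to 85% of a Week 240 effect that grows linearly

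*SAP*

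**What the plan says.** SAP 7.12.4.1 lists two between-arm analyses of vMRI.

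- **ANCOVA.** "Analysis of the change from baseline to endpoint of each vMRI parameter will be done", with baseline value, treatment, age, education, APOE4 carrier status and baseline florbetapir cortical SUVr as fixed effects. It is listed first and is the only one in that section with a stated null hypothesis: "The null hypothesis is that the difference in least square mean between the solanezumab group versus placebo equals zero". No time point is named there and endpoint is not defined there. The general rule in SAP 7.1 therefore applies: "End point is the last non-missing post-baseline measurement".
- **Slope analysis.** Because the pandemic separated visit from time, "an analysis treating time as a continuous variable will be conducted". Each parameter is regressed on time, treatment, APOE4 status and age with a common intercept, and slopes are compared between arms.

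Table A4.SAP.2 (SAP 7.5) lists "florbetapir parameters, plasma parameters, vMRI parameters, CSF parameters" for the mITT population and the same set for completers.

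On the protocol side, the MRI row of Attachment 1 has post-baseline scans at Visits 9, 27, 48 and 66 (Weeks 12, 84, 168 and 240) and at early termination. The last scheduled scan has some latitude: "The V66 MRI may be done up to 4 weeks before other V66 procedures". An early-termination visit is encouraged rather than assured (Protocol 8.4.1), and a schedule footnote allows some of its procedures to be left out. Protocol 11.2.9.3 says only "Change in vMRI data after treatment will be compared between treatment groups".

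**The concern.** Brain volumes change progressively (the listed ventricular volume in the opposite direction), so how much change a scan shows depends on when it was taken. Under the SAP 7.1 definition, a participant who leaves at Week 80 enters the ANCOVA with an exit scan at about Week 80 if one is done, or with the Week 12 scan if not, beside others scanned at Week 240. This is last observation carried forward, and nothing in the model adjusts for it.

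Two consequences follow. A true effect that grows over time is diluted, so the estimate cannot be read as the effect at the end of treatment. And if one arm loses more participants, or loses them earlier, that arm shows less atrophy even when the drug does nothing. The comparison serves the secondary objective on volumetric MRI (SAP 5.2).

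**Working it through.** **Inputs from the documents.** Scans at Weeks 12, 84, 168 and 240 plus early termination (Protocol Attachment 1); about 575 per arm (SAP 6.1); 30% attrition (SAP 6.2).

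**Assumptions.** Dropout uniform over 240 weeks, effect linear in time, and the decline, SD and arm-specific dropout used below. The documents give no vMRI mean change, SD or effect size.

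**The plan's own figure.** There is none for vMRI. The only one is 80% power for the PACC, and reproducing it checks how the 30% is used. A two-sample test on 575 × 0.7 = 402.5 completers per arm gives 75.4%. An MMRM with 10 post-baseline visits, attrition building linearly to 30% and compound-symmetric correlation 0.5 gives 80.2%, with a detectable difference of 0.530 against the stated 0.532. Reading the 30% as loss accruing up to Week 240 therefore fits; the covariance form is my assumption.

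**Dilution, no exit scans.** Shares of dropouts by last scan:

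- none: 12/240 = 5%
- Week 12: 72/240 = 30%
- Week 84: 84/240 = 35%
- Week 168: 72/240 = 30%

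Mean fraction of the Week 240 effect carried by dropouts = (0.30×12 + 0.35×84 + 0.30×168)/240 = 83.4/240 = 0.3475.

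Ratio to the Week 240 effect = (0.7 + 0.3×0.3475)/(1 − 0.3×0.05) = 0.80425/0.985 = **0.816**.

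**Dilution, every dropout scanned on leaving.** 0.7 + 0.3×0.5 = **0.85**.

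**Other patterns at 30% dropout.** From early to late dropout the ratio runs from 0.78 to 0.90 for a linear effect, and from 0.74 to 0.85 for an effect growing with time squared. An effect that is constant from the first scan is not diluted.

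**False difference with an inert drug.** With dropout d, the fraction of the full decline seen is f(d) = (1 − 0.6525d)/(1 − 0.05d) without exit scans, or 1 − 0.5d with them. The bias is the difference in f between arms. For 25% against 35% without exit scans it is 0.847 − 0.785 = 0.062 of the decline. The standard error in SD units is √[1/(575×0.9875) + 1/(575×0.9825)] = 0.0594. If the mean decline is 1 SD, z = 0.0621/0.0594 = 1.045, and the two-sided rejection rate is 18.1%. The same calculation elsewhere gives:

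| Dropout by arm | Exit scans | Bias, share of decline | Rejection rate at mean decline 0.5 / 1 / 2 SD |
|---|---|---|---|
| 30% / 30% | none or all | 0 | 5.0% / 5.0% / 5.0% |
| 27.5% / 32.5% | none | 0.031 | 5.8% / 8.2% / 18.1% |
| 27.5% / 32.5% | all | 0.025 | 5.5% / 7.1% / 13.6% |
| 25% / 35% | none | 0.062 | 8.2% / 18.1% / 55.2% |
| 25% / 35% | all | 0.050 | 7.1% / 13.6% / 39.6% |

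**Simulation** (1,500 trials, 575 per arm). With a true effect of 0.20 SD and 30% dropout in each arm, the last-scan ANCOVA estimates 0.165. An ANCOVA on Visit 66 completers and a slope analysis of all scans with cluster-robust errors both estimate 0.203. With no effect and equal dropout, rejection is 5.1%, 5.0% and 4.6% respectively. With no effect and 25%/35% dropout, the last-scan ANCOVA rejects 19% of the time at a decline of 1 SD and 47% at 2 SD, while the other two stay at about 5%.

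**The case against.** The strongest reply is that SAP 7.12.4.1 does not rest on the ANCOVA alone. The slope analysis uses scan time and carries nothing forward, and a version of it held its error rate in the simulation above. Completers are reported too, and their last scan is essentially the Visit 66 scan. A reader might infer that the whole vMRI comparison is a last-value analysis; the SAP does not support that.

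The mitigation is only partial. The slope analysis is introduced as an addition and is not ranked above the ANCOVA. It omits education and baseline SUVr. It does not say how repeated scans within a participant are handled, whereas the simulated version used cluster-robust errors. The completers set is selected on an event after randomization, and SAP 7.9.2.3, which gives the completer model, does not list vMRI.

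Two further points stand as limits on size. An MRI is scheduled at early termination, so 82% is the no-exit-scan case. And the documents do not say that every MRI yields volumes: if Week 12 did not, the ratio without exit scans would be (0.7 + 0.3×79.8/240)/(1 − 0.3×0.35) = 0.89.

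A reader might also see a conflict between protocol and SAP, because the protocol writes "an exception is the MRI at endpoint (Visit 66), which should be done according to the Study Schedule". That label occurs only in the rule for substituting dose-escalation safety MRIs. The protocol's vMRI objective and analysis text set no time point, so the difference is one of labels.

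**Conclusion.** The point holds for the first-listed ANCOVA. As SAP 7.1 and 7.12.4.1 stand, it mixes scans from Week 12 to Week 240 without adjusting for time. Under 30% uniform dropout and linear growth it estimates about 82% to 85% of the Week 240 effect. A false difference needs unequal dropout or unequal last-scan timing together with ongoing atrophy. The tabulated rates illustrate this and do not predict this trial, because the decline, variance and imbalance are assumed.

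A reader might infer a general loss of power, but the evidence does not support one. One set of assumed variances (mean decline 1 unit, slope SD 0.6, scan-error SD 0.25, true effect 0.10) gave 51% for the ANCOVA against 60% for a repeated-measures model. The simulation above gave 82% for the ANCOVA, 83% for slopes and 78% for Visit 66 completers. The dilution of the estimate appears in both.

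Nor does the point extend to amyloid PET or CSF. They share the endpoint wording but have one scheduled post-baseline time, and nothing was calculated for them here. The primary PACC analysis is unaffected. This is a change that should be made to one secondary comparison.

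**What to change.** In SAP 7.12.4.1, make the main vMRI treatment comparison a repeated-measures model with:

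- all post-baseline volumetric scans at their actual times, and the baseline scan as part of the outcome with arm means constrained equal at baseline;
- a stated within-participant covariance;
- the ANCOVA's remaining covariates: age, education, APOE4 carrier status and baseline florbetapir cortical SUVr;
- the treatment contrast at Week 240.

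Keep the last-value ANCOVA as a sensitivity analysis only. SAP 7.12.2.1 already uses a continuous-time model contrasted at 240 weeks for tau PET, so the approach is not new to the plan. Using actual scan times also accommodates the hiatus of up to 9 months described in SAP 6.1.

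The cost is SAP wording, a little more code and a slightly larger standard error: 0.046 against 0.042 in the simulation with slope SD 0.6. No further scans are needed. The model relies on dropout being explained by the observed data.
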